5.8 Drug counting and drug compliance judgment of subjects

During each follow-up visit, the observer should check the remaining empty boxes of the subjects, ask whether they take the drugs on time and in quantity, whether they are missing, missing or undertaking, and record them in the case report form in time for judging the compliance of clinical medication.

In the course of clinical trials, the compliance of subjects is mainly prescribed medication. The subjects should be strictly prescribed medication to avoid self-imposed other treatment methods.

Compliance of test medication=(dosage-not-dosage)/dosage x 100%

5.9 Regulations on combined use of drugs

1. In addition to experimental medication, nitroglycerin tablets can be used to alleviate symptoms when angina attacks. For drugs already used to treat coronary heart disease before inclusion, such as antiplatelet drugs, angiotensin-converting enzyme inhibitors (ACEI) or angiotensin II receptor antagonists (ARB), statins, calcium antagonists, beta-blockers and long-acting nitrates, the original varieties and dosages can be continued without adjustment. During the study period, it is forbidden to add any other Chinese and Western medicines which have therapeutic effects on angina pectoris of coronary heart disease.

2. For the original and emerging diseases requiring drug treatment, the drug combination should be recorded in the medical record and CRF in detail, including the generic name of the drug, dosage and method of administration, the starting time of drug use and the reasons for its use.

6. Observation items

6.1 General record items

Drug number, center code, subject name, start date, etc.

6.2 Observation index

6.2.1 General observation indicators

- 1) Demographic characteristics: gender, age, height, weight, etc.
- 2) Medical history, course of disease, treatment history, allergic history, complications and medication, etc.
- 3) Other screening indicators: urinary pregnancy test (women of childbearing age).

6.2.2 Effectiveness indicators

Main effective indicators: the efficacy of angina symptoms.

Secondary effectiveness indicators:

- (1) Curative effect of TCM syndromes;
- (2) Grading changes of severity of angina pectoris;
- (3) Changes in the number of angina attacks per week;
- (4) Nitroglycerin dosage;
- (5) Seattle Angina Scale score;
- (6) Blood HCY: The changes of blood HCY before and after treatment were compared between the two groups.
- (7) Incidence of cardiovascular events (sudden cardiac death, acute myocardial infarction, heart failure, percutaneous transluminal coronary angioplasty, coronary artery bypass grafting, malignant arrhythmia, cardiogenic cerebrovascular accident, angina pectoris requiring hospitalization, etc.).

6.2.3 Safety indicators

- (1) adverse event
- (2) vital signs: (blood pressure, body temperature, breathing and heart rate after 10 minutes' rest);
- (3) Routine safety laboratory examinations: blood routine (RBC, WBC, HGB, PLT), urine routine (ERY, LEU, PRO), stool routine (containing occult blood), liver function (ALT, AST, ALP, TBIL, GGT), renal function (BUN, Cr), coagulation (PT, APTT, FIB, TT)

6.2.4 Other observational indicators

- (1) Fasting blood glucose: The changes of fasting blood glucose before and after treatment were compared between the two groups.
- (2) Four items of blood lipid: The changes of four items of blood lipid before and after treatment were compared between the two groups.

6.3 Observation window

12 weeks \pm 4 days.

6.4 Test procedure

6.4.1 Visit 1-Import Period (-14 \pm 2 days)

- Obtain written informed consent
- Verification of selection/exclusion criteria for the import period
- Access to demographic information
- Obtain medical history, including concomitant medication
- Conduct a comprehensive physical examination
- Record concomitant medication
- Issuance of medication and diary cards during the introduction period
- ECG examination
- Record nitroglycerin dosage

6.4.2 Visit 2 - before treatment (0 days)

- Verification of selection/exclusion criteria
- TCM Symptom Score
- General information, main related symptoms and signs
- Record concomitant medication
- Subsequently, the experimental drugs were distributed in groups, and the remaining drugs were recovered and recorded.
- Physicochemical examination: blood routine, urine routine, stool routine + Occult blood, electrocardiogram, liver function (ALT, AST, ALP, GGT, TBIL), renal function (BUN, Cr), four items of coagulation, blood HCY, fasting blood sugar and blood lipid
- Major related symptoms and signs

- Seattle Angina Questionnaire
- Grading changes of severity of angina pectoris;
- Record nitroglycerin dosage
- Record adverse events

6.4.3 Visit 3 (4 weeks \pm 4 days)

- Fill in the syndrome integral form
- Major related symptoms and signs
- Seattle Angina Questionnaire
- Grading changes of severity of angina pectoris;
- Record concomitant medication
- Record adverse events
- Recovery of surplus drugs and distribution of experimental drugs
- Record nitroglycerin dosage
- Evaluation of curative effect

6.4.4 Visit 4 (8 weeks \pm 4 days)

- Fill in the syndrome integral form
- Major related symptoms and signs
- Seattle Angina Questionnaire
- Grading changes of severity of angina pectoris;
- Confirmation of the subjects' return of unused research drugs
- Record concomitant medication
- Record adverse events
- Record the dosage of nitroglycerin
- Evaluation of curative effect

6.4.4 Visit 5 (12 weeks \pm 4 days)

- Fill in the syndrome integral form
- Major related symptoms and signs
- Seattle Angina Questionnaire
- Grading changes of severity of angina pectoris;
- To confirm that the subjects returned untreated research drugs;
- Record concomitant medication
- Record adverse events
- ECG examination
- Physicochemical examination: blood routine, urine routine, stool routine + Occult blood, electrocardiogram, liver function (ALT, AST, ALP, GGT, TBIL), renal function (BUN, Cr), four items of coagulation, blood HCY, fasting blood sugar and blood lipid
- Record the dosage of nitroglycerin
- Evaluation of curative effect

7. Observation of adverse events

7.1 Recording of adverse events

In the research case history and case report form, "adverse event record form" is set up, which requires researchers to fill in the occurrence time, severity, duration, measures taken and outcome of adverse events truthfully. The relationship between adverse events and experimental drugs was also judged.

7.1.1 Definition of Adverse Event (AE)

It refers to adverse medical events that occur during a clinical trial when a subject receives a drug, but it does not necessarily have a causal relationship with the treatment. Specifically, it includes the following: suspicious adverse drug reactions, such as central nervous system, digestive system, hematopoietic system, rash, pruritus and other toxic and side effects; all reactions due to drug overdose, abuse, withdrawal, allergy or toxicity; apparently unrelated diseases, including the aggravation of pre-existing diseases; abnormal biochemical indicators of liver and kidney function. Abnormalities found by physical examination or physical examination and requiring clinical treatment or further examination (unlike repeated validation tests), etc. Abnormalities found in laboratory tests require clinical treatment or further investigation (unlike repetitive validation tests). If these abnormalities are related to reported events (e.g. elevated transaminase levels in jaundiced subjects), they should be described in the notes to the clinical event report and not included as a separate adverse event.

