Exclusion Criteria	
 1. Severe cardiopulmonary insufficiency (grade III, IV, severe abnormal pulmonary function); 2. Poor control of hypertension (systolic blood pressure (> 160 mmHg) or diastolic blood pressure (> 100 mmHg) after treatment; 3. Complicated with liver and kidney function damage, ALT, AST (> 1.5 times of the upper limit of normal value), or Cr (> the upper limit of normal value), combined with hematopoietic system and other serious primary diseases; 4. Acute myocardial infarction within 3 months after interventional therapy; 5. Cardiac pacemaker; 6. Pregnancy, lactation or pregnancy planning; 7. Anaphylactic constitution or allergic to known ingredients of research drugs; 8. Chest pain caused by other causes (moderate anemia, hyperthyroidism, etc.) 9. Those who participated in other clinical drug trials within one month; 10. According to the judgement of the researchers, it is not advisable to participate in clinical researchers. 11. Other factors affecting ST-T changes in ECG, such as myocardial hypertrophy, left bundle branch block, etc.
Sample size	
According to the statistical requirements, the sample size was estimated. The main effect index was the curative effect of angina pectoris symptoms treated for 12 weeks. According to the literature, the total effective rate of basic treatment plus placebo was 67.5%, and the total effective rate of basic treatment plus experimental drugs was predicted to be 84.3%. set $\alpha=0.05$, $1-\beta=0.2$, according to the experimental group: control group = 1:1 set up group,
 $n = \frac{P_1 \times (100 - P_1) + P_2 \times (100 - P_2)}{(P_2 - P_1)^2} \times f(a, b)$ 
The minimum sample size to meet the statistical requirements was

	98.4 cases in each group, and the dropping rate was not more than 20%, 120 cases in each group, a total of 240 cases.
Effectiveness evaluating indicator	1. Main outcome measures: The curative effect of angina pectoris; 2. Secondary indicators: curative effect of TCM syndromes, grading changes of severity of angina pectoris, changes of attack times per week, nitroglycerin dosage, score of Seattle Angina Scale and incidence of cardiovascular events, blood HCY (blood homocysteine).

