4.7 Subject exclusion criteria

1) Severe cardiopulmonary insufficiency (grade III, IV, severe abnormal pulmonary function);

2) Poor control of hypertension (systolic blood pressure (> 160 mmHg) or diastolic blood pressure (> 100 mmHg) after treatment;

3) Severe primary diseases such as ALT, AST (> 1.5 times the upper limit of normal value) or Cr (> upper limit of normal value), hematopoietic system and so on.

4) Acute myocardial infarction within 3 months after interventional therapy;

5) Other factors affecting ST-T changes in ECG, such as myocardial hypertrophy, left bundle branch block, etc.

6) Cardiac pacemaker;

- 7) Chest pain caused by other causes (moderate anemia, hyperthyroidism, etc.);
- 8) Pregnancy, lactation or pregnancy planning;
- 9) allergic constitution or allergic to known ingredients of research drugs;
- 10) Those who participated in other clinical drug trials within one month;
- 11) Researchers consider it inappropriate to participate in clinical research.

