7.1.4 Treatment of subjects with adverse events

When adverse events occur, researchers can decide on the measures to be taken according to their condition. Generally, the following methods are adopted:

- (1) observation without discontinuing the drug test;
- (2) observation and discontinuation of the drug test without remedial treatment;
- (3) discontinuation of the drug test with remedial treatment.

All adverse events should be tracked and investigated, and the treatment process and results should be recorded in detail until the subjects are properly resolved or the condition is stable. Those with abnormal laboratory indicators should be tracked back to normal or pre-medication level. According to the severity of adverse events, follow-up methods can be used to select hospitalization, outpatient service, home visits, telephone and other forms.

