(12) Safety analysis: 2 test was used to compare the incidence of adverse events in the two groups, and list the adverse events in the study; analysis of the normal/abnormal changes of laboratory results before and after the study and the relationship between abnormal changes and research drugs.

11. Quality Control and Guarantee of Clinical Trials

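### Laboratory safety is analysed as normal/abnormal before and after, although subjects can enter with raised liver tests, so no stated between-arm comparison shows worsening from a raised baseline or the size of a rise

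*Protocol*

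**What the plan says.** **Entry.** Protocol 4.7, item 3, excludes "ALT, AST (> 1.5 times the upper limit of normal value) or Cr (> upper limit of normal value". The abstract gives the same ALT/AST limit. Neither place gives a numeric limit for ALP, GGT, TBIL or BUN.

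**Measurement.** All seven tests are taken at Visit 2 (6.4.2, day 0) and Visit 5 (12 weeks). The visits at 4 and 8 weeks schedule no laboratory tests.

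**Analysis.** Section 10.2.3(12) specifies "analysis of the normal/abnormal changes of laboratory results before and after the study", together with the relation of abnormal changes to the study drug, a test of adverse-event incidence, and a listing of events.

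**Adverse-event definition.** Section 7.1.1 lists "abnormal biochemical indicators of liver and kidney function" without qualification. Shortly after, it has a separate laboratory sentence: "Abnormalities found in laboratory tests require clinical treatment or further investigation". For diseases it refers to "apparently unrelated diseases, including the aggravation of pre-existing diseases".

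**Follow-up.** Section 7.1.4 has abnormal laboratory indicators "tracked back to normal or pre-medication level".

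**The concern.** Safety is half of the stated purpose of the trial, and scheduled laboratory safety rests on one contrast, day 0 against week 12. A two-state classification serves that contrast well only if nearly everyone starts normal and any crossing of the limit matters equally. The entry rule does not secure the first condition for the liver tests or BUN, and the second does not hold for any test.

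Two things are at stake. A subject already above the limit has nowhere worse to go in the table, so a deterioration in that group produces no shift. And the table cannot separate many trivial crossings in one arm from a few large ones in the other.

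Section 7.1.1 adds a recording problem. Sites could differ on whether a raised value that is unchanged or better than on day 0 is an adverse event.

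**Working it through.** The protocol states no figure for this point, so there is none to reproduce. The check applies its rules to example values. Values are multiples of the upper limit of normal (ULN) and are illustrations; none comes from the protocol.

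**Rules**
- Entry for ALT/AST (4.7): admitted if day-0 value ≤ 1.5.
- State for the analysis (10.2.3(12)): abnormal if value > 1, otherwise normal.
- Liver/kidney clause in 7.1.1, read literally: an adverse event if the on-treatment value > 1.

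| Day 0 → week 12 | Can enter | Cell in normal/abnormal table | Change (× ULN) | Literal 7.1.1 clause |
|---|---|---|---|---|
| 1.2 → 8 | yes | abnormal → abnormal | +6.8 (ratio 6.67) | met |
| 1.4 → 1.1 | yes | abnormal → abnormal | −0.3 | met |
| 1.4 → 0.9 | yes | abnormal → normal | −0.5 | not met |
| 0.9 → 1.1 | yes | normal → abnormal | +0.2 | met |
| 1.0 → 8 | yes | normal → abnormal | +7.0 | met |

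Rows 1 and 2 share a cell although one is a large rise and the other a fall. Rows 4 and 5 share a cell although the rises differ by 6.8 × ULN.

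**Which tests.** Worsening from a raised baseline is hidden for ALT, AST, ALP, GGT, TBIL and BUN. It does not arise for Cr, because a value above the limit is excluded. The loss of degree applies to all seven.

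**How many subjects.** The share abnormal at entry is not given. Assuming 5% to 15% with ALT or AST between 1 and 1.5 × ULN: 0.05 × 120 = 6 and 0.15 × 120 = 18 per arm who could not register worsening in the table.

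**Would means show it?** Section 10.2.3(4) describes measurements by mean and SD and compares them with baseline. If it covers laboratory values, the row 1 subject moves the mean of 120 by 6.8/120 = 0.06 × ULN, too little to notice.

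**The clauses on what counts, applied to 1.4 → 1.1**
- Liver/kidney clause of 7.1.1 read alone: counts, because the value is still abnormal.
- Treatment-or-investigation sentence of 7.1.1: does not count unless the value needs one of these.
- Aggravation wording of 7.1.1 for existing disease, applied by analogy: does not count, because the value is better.
- 7.1.4: the value is already below its pre-medication level, so follow-up would be complete as soon as it began.

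The first reading disagrees with the other three, and the protocol does not say which governs.

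**The case against.** Three stronger readings are tempting, and the documents do not support them.

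*That the protocol has no baseline reference for laboratory safety.* It has. Section 10.2.3(12) compares before with after, 10.2.3(4) compares measurements with baseline in general terms, and 7.1.4 uses the pre-medication level. What lacks a baseline condition is the liver/kidney clause of 7.1.1.

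*That a rise such as 1.2 to 8 × ULN would go unseen.* It would not. On either reading of 7.1.1 it would be expected to be an adverse event, recorded, followed up, counted and listed. Section 11.1 requires markedly high values to be verified and explained. Section 10.2.1(5) provides for maximum, minimum and median in general terms, and a maximum would show one extreme value. This stands, and it limits the point to the between-arm laboratory comparison. It does not remove it. The listing and the physician's check are not comparisons of degree. A maximum says nothing about how many subjects rose or from where. Severity in 7.1.2 is graded by effect on daily activities, so a symptomless enzyme rise would most naturally be graded mild.

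*That improving values are counted as adverse events, which dilutes the comparison of arms.* This needs the most literal reading of one item in a translated list, while the surrounding text points the other way. It is an ambiguity, not a fixed counting rule. Any dilution figure would need assumed rates and the worst case of that reading. Even with 10% abnormal at entry and new-event rates of 5% and 10%, recorded rates would be 1 − 0.90 × 0.95 = 14.5% and 1 − 0.90 × 0.90 = 19.0%: a difference of 4.5 points instead of 5.0. No dilution is claimed here.

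Finally, shift tables in bands are commonly left to the statistical analysis plan, which is not at hand, and 10.2.3(12) does not say that normal/abnormal is the only summary. Their absence alone is therefore no finding. The point is that the protocol itself names a two-state analysis that fits badly with its own entry rule.

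**Conclusion.** The point holds in limited form. The laboratory comparison named in 10.2.3(12) cannot register worsening in a subject who is abnormal on day 0, and it gives every crossing of the limit the same weight. Section 4.7 makes the first case possible for ALT, AST, ALP, GGT, TBIL and BUN. Large rises would still reach the adverse-event listing; what is missing is a stated comparison between arms that shows their degree.

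The size cannot be fixed from the protocol. The 6 to 18 subjects per arm rest wholly on the assumed 5% to 15% abnormal at entry. The loss of degree among subjects who start normal needs no such assumption.

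The wording of 7.1.1 is a secondary point: clauses to be reconciled, not proof that events will be miscounted. The whole is a modest defect, worth correcting because the correction costs so little.

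**What to change.** 1. In 10.2.3(12), keep the normal/abnormal table and add, for ALT, AST, ALP, GGT, TBIL, BUN and Cr, a table by arm of day-0 against week-12 values in multiples of the centre's upper limit, with any unscheduled values included. Analysis bands could be, for example, up to 1, above 1 to 1.5, above 1.5 to 3, above 3 to 5, and above 5. Report the number of subjects per arm who move up a category and the difference between arms.
2. In 7.1.1, reconcile the liver/kidney clause with the sentence on abnormalities needing treatment or further investigation and with the pre-medication reference in 7.1.4, so that a value unchanged or improved from day 0 is not counted as a new adverse event.

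The cost is wording and one table per test. Day-0 and week-12 values are already scheduled, and 11.5 already requires each unit to supply its normal ranges. The 7.1.1 change should reach sites before recording starts, because it governs what they enter on the case report form.

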7.1.2 Judgment of Causality between Adverse Events and Testing Drugs

In the event of adverse events, the researcher decides the diagnosis and treatment measures based on the condition of the patient and whether to discontinue the observation. In case of serious adverse events, the unit undertaking clinical research should take necessary measures immediately to protect the safety of the subjects. If the duration of the trial is more than 4 weeks, the subjects will quit because of the aggravation of the illness (increased number of attacks, prolonged duration of attacks, increased degree of pain, increased dosage of nitroglycerin or increased level of attacks). Such cases need to be included in PPS statistics as non-curative cases. Researchers should record the relevant information in detail on the medical records of scientific research.

Criteria for grading the severity of adverse events

Mild: Usually temporary and does not affect normal daily activities.

Moderate: quite uncomfortable, can affect normal daily activities.

Severity: unable to carry out normal daily activities.

Judgment of causality with drugs:

1) Causal judgment indicators of adverse reactions:

Item 1: Whether there is a reasonable relationship between the time of starting medication and the time of suspicious occurrence;

Item 2: Does the suspicious adverse reactions conform to the known types of adverse reactions of the drug?

Item 3: Whether the suspected adverse reactions can be explained by the patient's pathological condition, combination of medication, therapy or previous therapy;

Item 4: Does the suspicious adverse reaction decrease or disappear after withdrawal or dose reduction?

Item 5: Does the same reaction reappear after the suspicious drug is used again?

Causality criteria: according to the above five judgment indicators to determine the order.

Causal Judgment of Adverse Reactions

Result	Judgement index				
	item1	item 2	item 3	item 4	item 5
Definitely related	+	+	—	+	+
Vey kikely related	+	+	—	+	?
Probably related	+	+	±	±	?
May be irrelevant	+	—	±	±	?
Impossibly related	+	—	+	—	—

Explanation: +yes、—no、±not sure、? unknown。

2) Based on the above table, the relationship between the following five levels of adverse events and drugs was determined.

①Definitely related; ②Vey kikely related; ③Probably related; ④May be irrelevant; ⑤Impossibly related。

The total number of cases with 1+2+3 was used as the molecule to calculate the incidence of adverse reactions, and all the selected cases for adverse reactions

evaluation were used as denominators.

7.1.3 Recording and reporting of adverse events

Researchers should explain to the subjects that they should truthfully reflect the changes of their condition after medication, but avoid induced questions. While observing the curative effect, we should pay close attention to adverse events or unexpected side effects (including symptoms, signs, laboratory tests), analyze the causes, make judgments, and follow up observation and record.

For adverse events during the trial, the researchers should record the occurrence time, symptoms, degree, duration, treatment measures and outcome in the case report form, judge the correlation between the adverse events and the test drugs, sign and date them.

7.1.4 Treatment of subjects with adverse events

When adverse events occur, researchers can decide on the measures to be taken according to their condition. Generally, the following methods are adopted:

- (1) observation without discontinuing the drug test;
- (2) observation and discontinuation of the drug test without remedial treatment;
- (3) discontinuation of the drug test with remedial treatment.

All adverse events should be tracked and investigated, and the treatment process and results should be recorded in detail until the subjects are properly resolved or the condition is stable. Those with abnormal laboratory indicators should be tracked back to normal or pre-medication level. According to the severity of adverse events, follow-up methods can be used to select hospitalization, outpatient service, home visits, telephone and other forms.

